to insulin resistance. The sum of all sarcolemmal disaturated 1,2-DAG species were significantly greater in T2D compared to lean volunteers (Figure 2A), and was inversely related to insulin sensitivity (Figure 2B). Notably, 1,3-disaturated DAG content was not different between groups revealing isomer specificity. We previously showed that membrane di-saturated DAG content predicted PKC activation and insulin resistance (26). These data agree and suggest that sarcolemmal DAG containing saturated acyl side chains represent membrane accumulation of DAG that is particularly negative for insulin sensitivity.

PKC ϵ activity is increased in obesity and T2D. We

measured the membrane/cytosol ratio of PKC ϵ , which is commonly used as a surrogate for PKC activity. We found significantly greater PKC ϵ activation in obese and T2D subjects compared to lean controls (Figure 3), with no significant differences found for PKC β II, δ , and θ isoforms. These data are consistent with greater PKC activation from sarcolemmal DAG accumulation.

Sarcolemmal C18:0 ceramide accumulates in insulin resistance. Of the 9 sarcolemmal ceramide species measured, only C18:0 ceramide was significantly greater in T2D compared to lean (Figure 4A), and was inversely related to the rate of glucose disappearance during an insulin clamp (Figure 4B). In a pilot study sarcolemmal C18:0 ceramide decreased by 21% after a combined weight loss

and exercise training intervention. These data parallel a recent publication by our lab showing C18:0 muscle ceramides significantly related to insulin resistance in a different cohort (27). C18:0 ceramide antagonizes an inhibitor of PP2A, resulting in increased PP2A activity (28). Combined, these data suggest that sarcolemmal C18:0 ceramide may promote insulin resistance, and due to the location may explain the canonical pathways of ceramide induced insulin resistance, including activation of PP2A activity, and inhibition of AKT phosphorylation in response to insulin.

Mitochondrial/ER ceramide accumulates in insulin

resistance. Mitochondrial ceramide content was greater in T2D compared to lean individuals, which is largely explained by C22:0 and C24:0 species (Figure 7A). Total ceramide content was inversely related to

insulin sensitivity (Figure 7B). These data are consistent with the hypothesis that mitochondrial ceramides promote insulin resistance.

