Mitochondrial/ER ceramides decrease after insulin sensitizing lifestyle intervention - Pilot data for a combined weight loss/exercise training intervention show decreased whole cell ceramide content, as shown before (11; 15) (Figure 8). However, the decrease in whole cell ceramide content comes only from a decrease in mitochondrial/ER ceramide. These data point to an important role of mitochondrial/ER ceramides on insulin sensitivity in vivo.

Mitochondrial/ER DAG accumulates in lean insulin sensitive individuals. Preliminary data show mitochondrial/ER 1,2- and 1,3-DAG were

Figure 2. Sarcolemmal di-saturated DAG content by group (A), and by insulin sensitivity (B) in lean, obese, and type 2 diabetics. Values are means +/- SEMC # significantly different than lean, p<0.05.

Figure 3. PKCE activation in lean, obese, and type 2 diabetics. Values are means +/- SEM. #= significantly different than lean, p<0.05.

Figure 4. Sarcolemmal C18:0 ceramide content by group (A), and by insulin sensitivity (B) in lean, obese, and type 2 diabetics. Values are means +/- SEM. #= significantly

different than lean, p < 0.05.

higher in lean individuals compared to obese or type 2 diabetic volunteers (Figure 9), with the greater DAG content distributed over most species. These data are counterintuitive, but may reflect the greater content of mitochondria in lean individuals compared to obese volunteers with and without diabetes, and/or increased mitochondrial fission/fusion (29; 30).

Mitochondrial/ER DAG increase after weight loss and exercise training.

Preliminary data from a weight loss and exercise training intervention show an increase in mitochondrial/ER 1,2-DAG after the intervention (Figure 10). These data are consistent with some reports in the literature where DAG concentration was increased in endurance trained athletes (13). These data agree with Figure 9 and suggest mitochondrial/ER DAG accumulation may be a previously unrecognized adaptation to exercise training and/or weight loss.

Insulin resistant muscle accumulates long chain acyl-carnitines and shows oxidative

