Obese men and women (BMI 30-40 kg/m²) will be recruited for this study who are between 30-50 years of age and sedentary (<2 hours/week of planned physical activity). Individuals with normal glucose tolerance (NGT), pre-diabetes, and newly diagnosed type 2 diabetes will be enrolled. Normal glucose tolerance is defined as a HbA1c of <5.7%, pre-diabetes as a HbA1c of 5.7-6.4%, and type 2 diabetes as a HbA1c of \geq 6.5% (31). Oral contraceptive use is allowed as long as women don't change their use, or lack thereof, during the course of the study. Exclusion criteria include: regular exercise more than 2 hours/week, medications that could affect glucose, lipid metabolism, thyroid disease, a history of lung disease, pregnancy, active cigarette smoking and severe plasma lipid disorders.

Inclusion criteria:

BMI: 30-40 kg/m²
Age: 30-50 years
Planned physical activity: <2 hrs/week
Glucose tolerance: NGT, pre-diabetes, and Type 2 diabetes
Normal glucose tolerance (NGT) is defined as HbA1c of <5.7%, pre-diabetes as HbA1c of 5.7-6.4%, and type 2 diabetes as HbA1c of ≥6.5% (31).
Oral contraceptive use: Yes or No as long as there is no change during the study
Medications: not taking TZD's, insulin
Thyroid status: TSH between 0.5-5.0 mU/L
Pregnancy status: Not pregnant
Nonsmoker (tobacco and any form of marijuana use)
Fasting TG <400mg/dl
FSH < 20 IU/L

C. Study Design and Research Methods

Ninety-two individuals (30-50 years old) will be screened to recruit sixty-nine obese men and women into the study. Individuals with and without prediabetes will be recruited to achieve a range of starting insulin sensitivities without confounding effects of medications used to treat type 2 diabetes. Volunteers will undergo an insulin clamp before and after block randomization by sex and pre-diabetes strata equally across intervention groups, into a three month

intervention consisting of: 1) endurance exercise training without weight loss, 2) diet-induced weight loss, or 3) delayed intervention control (Figure 5). The three month intervention will result in significant gains in fitness, weight loss, and improvements in insulin sensitivity, but is short enough to maximize retention.

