Every attempt will be made to minimize the risks involved to patients in this study. Subjects privacy, autonomy and confidentiality will be protected with redundant IRB & HIPAA-compliant measures. Subjects may withdraw from the study at any time. Only state-of-the-art techniques will be used in a NIH-funded, JCAHO accredited CTRC facility. CTRC personnel are exquisitely trained, and emergency equipment is easily accessible on-site. Universal precautions will be taken to protect everyone involved with subject testing. Sterile technique is invoked where appropriate. All infusion are prepared and stored by a licensed pharmacist and tested for sterility and pyrogenicity. We will also have an independent safety officer who will evaluate subject risk annually. Taken together, these measures have proven successful in the minimization of risk to subjects. Protected and de-identified information will be kept on password-protected computer systems with hard copies in locked filing cabinets in locked offices.

E. Potential Scientific Problems:

We have extensive experience recruiting individuals across the metabolic spectrum (51-55), as well as performing insulin clamps (39; 51; 56; 57), and muscle biopsies (26; 43; 51; 53; 58-61) and therefore no problems are expected with the proposed studies. An alternative approach to our proposal would be to use a combined exercise and weight loss intervention, which may have more dramatic results compared

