Aim 1: Our statistical methods are rigorous with an a priori statistical analysis plan to test our hypothesis in an unbiased manner, and power analysis based on our own preliminary data. Prior to analysis, data will be analyzed for normality, and any non-normally distributed variables will be log-transformed for use in analytic models. Correlations between the change in sarcolemmal DAG and sphingolipid species and the change in insulin sensitivity will be performed using Pearson's correlation coefficients in the entire study group (n=51). Then, data comparing changes in sarcolemmal DAG and sphingolipid species to changes in insulin sensitivity before and after the intervention will be analyzed using a one-way Analysis of Variance (ANOVA) to examine overall differences between the intervention groups, and using Tukey's procedure to make pair-wise comparisons (e.g control vs. exercise, control vs. diet only) while adjusting for multiple comparisons. Changes in individual DAG and ceramide species will be examined using the Benjamini Hochberg procedure to limit false discoveries (62), and then Principal Component Analysis (PCA) will be used to examine groups of DAG and ceramide species (13). Analyses will be conducted using SAS statistical software ver. 9.4 (Cary, NC). The power analysis is based on changes in sarcolemmal lipids assuming there will be no significant changes in the control intervention. With an overall n of 51, we will have 92% power to detect a Pearson correlation coefficient similar to our preliminary data (Figure 2B, r= -0.45), and 80% power to detect a correlation coefficient as small as -0.38. Pilot data showed sarcolemmal C18:0 ceramide decreased 0.041 ng/ug protein with a SD of .02 after the combined intervention. With an n of 17/group we will have 84.6% power to measure a similar change in sarcolemmal DAG and sphingolipids for individual group comparisons using the Tukey procedure. The type 1 error rate (alpha) will be set at 5% for all comparisons.

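### The 84.6% pairwise power stated for Aim 1 cannot be reproduced from the inputs printed beside it, which give 99.97%

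*Combined protocol and SAP*

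**What the plan says.** The Aim 1 part of section IV.F gives one pilot result for the group comparisons: "Pilot data showed sarcolemmal C18:0 ceramide decreased 0.041 ng/ug protein with a SD of .02 after the combined intervention". The next sentence draws the power from it: "With an n of 17/group we will have 84.6% power to measure a similar change in sarcolemmal DAG and sphingolipids", for individual group comparisons by Tukey's procedure. The same paragraph states that the power analysis is made "assuming there will be no significant changes in the control intervention", that alpha is 5% throughout, and that a one-way ANOVA of changes is followed by "pair-wise comparisons (e.g control vs. exercise, control vs. diet only) while adjusting for multiple comparisons".

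Section IV.C names the three randomised groups: "1) endurance exercise training without weight loss, 2) diet-induced weight loss, or 3) delayed intervention control". The combined intervention that produced the pilot change is not among them. Section IV.E discusses it as an alternative, a "combined exercise and weight loss intervention, which may have more dramatic results compared" with exercise or weight loss alone.

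For Aim 1, no other change, SD, correlation between visits or pilot sample size is given for the group comparisons. The only smaller effect with a stated power is a correlation of -0.38 across all 51 participants.

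**The concern.** A pilot change of twice its SD is very large for a comparison with 17 per group, and power should be close to 100%. A stated 84.6% is well below that, so at least one number in the two sentences is not the one that was used.

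Sarcolemmal C18:0 ceramide is a primary outcome of Aim 1, and this is the only power stated for Aim 1's between-group comparisons. As printed, a reader cannot tell which lipid, difference and SD stand behind it. That matters most for effects smaller than the pilot's, where the power of the exercise and diet contrasts depends heavily on which SD is correct.

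**Working it through.** **Inputs** (all from section IV.F, Aim 1, except the number of groups, which is from section IV.C)

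- Change in the active group: 0.041 ng/ug protein. Change in control: 0.
- SD: 0.02, read as the SD of the change.
- Three groups of 17, so the error df are 51 - 3 = 48.
- Tukey at 5%. Sidedness is not stated; Tukey's procedure is two-sided.

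**Attempt to reproduce 84.6%**

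- Standardised difference: d = 0.041 / 0.02 = 2.05.
- Critical |t| = q(0.95; 3, 48) / √2 = 3.420 / 1.414 = 2.418.
- Noncentrality = d × √(n/2) = 2.05 × √8.5 = 5.98.
- Power = P(|T| > 2.418), with T noncentral t on 48 df and noncentrality 5.98, which is **99.97%**. The plan states 84.6%.

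**Other readings of the same inputs**

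| Reading | Power |
|---|---|
| Least favourable rounding (0.0405 / 0.025 = 1.62) | 98.8% |
| Bonferroni for three pairs, 48 df | 99.97% |
| Scheffé | 99.96% |
| Both active arms jointly significant against control | 99.95% |
| 13 per group (dropout taken off a second time) | 99.6% |
| 0.02 as a per-visit SD, zero correlation (SD of change 0.02 × √2 = 0.0283) | 96.1% |
| 7 per group | 88.8% |
| 6 per group | 81.6% |

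None gives 84.6%, and no whole number per group does so at d = 2.05.

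**What would give 84.6% with 17 per group**

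Solving the same formula for a power of 84.6% gives d = 1.185. That means either

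- an SD of change of 0.041 / 1.185 = 0.0346, if the change is right; or
- a change of 1.185 × 0.02 = 0.0237, if the SD is right. This is 0.0237 / 0.041 = 58% of the pilot change.

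**Why the answer matters for smaller changes**

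The documents give no lipid change for exercise alone or diet alone, so the shares below are assumptions. Tukey, 17 per group:

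| Share of pilot change (assumed) | Difference | Power at SD 0.02 (printed) | Power at SD 0.0346 (implied by 84.6% at 0.041) |
|---|---|---|---|
| 100% | 0.041 | 99.97% | 84.6% |
| 75% | 0.0308 | 98% | 57% |
| 50% | 0.0205 | 71% | 26% |
| 25% | 0.0103 | 19% | 7% |

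A power of 80% needs d = 1.1225. That is a difference of 1.1225 × 0.02 = 0.0224 (55% of the pilot change) at the printed SD, or 1.1225 × 0.0346 = 0.0388 (95% of it) at the implied SD.

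**The case against.** **The power sentence is wider than its printed inputs.** It speaks of sarcolemmal DAG and sphingolipids, while 0.041 and 0.02 belong to C18:0 ceramide. The 84.6% may have been computed correctly for a more variable lipid. This stands: the documents show a figure that cannot be reproduced, not a proven miscalculation. But the missing input would then have to be stated.

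**The gap is in the cautious direction.** The plan claims less power than its inputs give, and the power for the correlations at n = 51 reproduces approximately (Fisher z: 91.9% for r = -0.45, 79.2% for r = -0.38). A reader might infer from the mismatch that 17 per group is too few. The documents do not support that. Nor do they support full reassurance, because the comfortable figures hold only at the SD that is in question.

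**A standard error printed as an SD.** This is tempting, since the Figure 4 legend for the same lipid reads "Sarcolemmal C18:0 ceramide content by group (A), and by insulin sensitivity (B) in lean, obese, and type 2 diabetics. Values are means +/- SEM". That legend describes a cross-sectional comparison of lean, obese and diabetic people, not the pilot change, and section IV.F says SD. A standard error of 0.02 from three subjects would give an SD of 0.02 × √3 = 0.0346 and 84.5% power, but from four subjects it would give 71%, and no pilot sample size is stated. It is a question for the investigators, not a finding.

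**The pilot's origin is disclosed.** A reader might infer that the plan passes off a combined-intervention effect as a single-intervention one. It does not. Section IV.F names the source, section III reports "In a pilot study sarcolemmal C18:0 ceramide decreased by 21% after a combined weight loss" and exercise training, and section IV.E acknowledges that the combination may do more. A smaller effect is also powered on the correlation scale. Power for smaller pairwise changes is therefore a useful addition, not the correction of an error.

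**Conclusion.** The point holds as a reporting error that should be fixed. The stated 84.6% does not follow from a change of 0.041, an SD of 0.02, no change in control, 17 per group and Tukey at 5%; those give 99.97%, and 98.8% at worst rounding. Either the SD or the power is misprinted, or an unstated input was used, and the documents cannot settle which.

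The recomputation assumes that 0.02 is the SD of change, that it is common to the groups, and that the test is two-sided. The multiplicity rules, per-visit SD and group sizes tried do not remove the gap. The result does not establish that the trial is under-powered. The figures for smaller changes are illustrations that rest on assumed shares and on an SD still to be confirmed.

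**What to change.** 1. Check the pilot data for the SD of change in sarcolemmal C18:0 ceramide and the number of subjects behind it, and confirm that the printed value is an SD.
2. Restate the Aim 1 sentence with the inputs actually used, correcting whichever of the SD or the 84.6% is wrong. For example: with 17 per group, Tukey's procedure at 5% (48 df) gives [x]% power for a difference from control of [difference] in [lipid species], with an SD of change of [SD].
3. Optionally, add one sentence with the pairwise power, or the minimum detectable difference, for exercise versus control and diet versus control at changes smaller than 0.041, using the confirmed SD. Until it is confirmed, show both columns of the table above and label the shares as assumptions.

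The cost is one check of existing pilot data, one recalculation and one or two sentences in section IV.F. Sample size, arms, outcomes and tests stay as they are.

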stress. Basal acyl-carnitines revealed accumulation of many long chain acyl-CoA's in type 2 diabetics including C18:0, C18:2-OH, and C20:4, which are thought to promote insulin resistance (Figure 11A). A significantly decreased GSH/GSSG ratio in type 2 diabetes individuals compared to lean volunteers suggest a more oxidized state, consistent with increased oxidative stress in insulin resistance (Figure 11B).

DAG and ceramide decrease mitochondrial

function. We administered 1,2-DAG, ceramide, dihydroceramide, and vehicle controls to isolated rat mitochondria in vitro to evaluate the impact on mitochondrial respiration using pyruvate and malate as substrates. DAG and ceramide decreased state 3 respiration, with no changes observed with dihydroceramide administration (Figure 12A and B). State 4 respiration did not change for 1,2-DAG and dihydroceramide, but increased significantly with increasing doses of ceramide. Both 1.2-DAG and ceramide decreased ADP/O ratios (Figure 13A and B), while dihydroceramide had no effect. These data indicate 1.2-DAG and ceramide reduced mitochondrial respiration and coupling, and are consistent with accumulation of mitochondrial lipids altering mitochondrial function.

Protocol Template CF-146, Effective 7/10/11

IV. Research Methods

A. Outcome Measure(s):

Primary outcomes:

Aim 1: Change in insulin sensitivity, change in sarcolemmal Di-C18:0 DAG and C18:0 ceramide, change in PKCepsilon and PP2A activity

Aim 2: Change in insulin sensitivity, change in mitochondrial/ER total DAG and ceramide content, change in state 3 mitochondrial respiration, change in GSH/GSSG, change in C18:0, C18:2-OH, and C20:4 acylcarnitines, change in GRP78

Aim 3: Change in mitochondrial state 3 and state 4 respiration in response to DAG and ceramide before and after lifestyle interventions

Secondary outcomes: Changes in other localized lipids and intracellular responses will be exploratory in nature. In addition, we will collect subjective and objective information about sleep and an exploratory analysis.

B. Description of Population to be Enrolled:

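### The 84.6% pairwise power stated for sarcolemmal DAG has no DAG input behind it, and it does not follow from the ceramide figures printed beside it

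*Combined protocol and SAP*

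**What the plan says.** Section IV.A (Outcome Measures) names as Aim 1 primary outcomes, among others, "change in sarcolemmal Di-C18:0 DAG and C18:0 ceramide". These are two lipids, each an outcome in its own right.

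Section IV.F (Data Analysis Plan, Aim 1) compares the three arms by one-way ANOVA with Tukey pairwise comparisons. Its power statement for those comparisons has these parts:

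- The input: "Pilot data showed sarcolemmal C18:0 ceramide decreased 0.041 ng/ug protein with a SD of .02 after the combined intervention".
- The claim, at 17 per arm: "84.6% power to measure a similar change in sarcolemmal DAG and sphingolipids for individual group comparisons using the Tukey procedure".
- The control arm: the calculation is made "assuming there will be no significant changes in the control intervention".
- The error rate: "The type 1 error rate (alpha) will be set at 5% for all comparisons".

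The sarcolemmal DAG results described in section III (Preliminary Studies) are cross-sectional: "The sum of all sarcolemmal disaturated 1,2-DAG species were significantly greater in T2D compared to lean volunteers", together with an inverse relation to insulin sensitivity. The caption of Figure 2 describes the same two displays. The one sarcolemmal before-and-after pilot result in that section is a 21% fall in C18:0 ceramide. The pilot DAG change that is described (Figure 10) is a rise in the mitochondrial/ER fraction.

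**The concern.** Power for a pairwise contrast depends on the expected difference in change divided by the SD of change for the variable tested. The input sentence supplies both quantities for C18:0 ceramide. The next sentence applies a power figure to DAG as well, with no DAG quantity in between. Di-C18:0 DAG is a different molecule with its own content and variability, and a ceramide change in ng/ug protein says nothing about it. The mitochondrial/ER DAG result cannot stand in, because it is another compartment and moves in the opposite direction to the fall in sarcolemmal DAG that Aim 1 hypothesizes.

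At stake is how the DAG half of the Aim 1 hypothesis can be read. If a DAG contrast is not significant, a reader who relies on the plan could take it as a result from a test with 84.6% power. The documents give no basis for that. The ceramide claim has a problem of its own, since a power figure that does not follow from its stated inputs cannot be checked or relied on.

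**Working it through.** **Inputs**

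- Completers per arm n = 17, three arms, 51 in total (sections IV.C and IV.F). Error df = 51 − 3 = 48.
- Change 0.041, SD 0.02, for C18:0 ceramide (section IV.F, Aim 1).
- Change in the control arm taken as 0 (section IV.F, Aim 1).
- Alpha 5%, Tukey (section IV.F, Aim 1). Sidedness is not stated; two-sided is assumed.
- Sarcolemmal DAG change and SD of change: none in the readable text.

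**Formula**

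The Tukey critical value on the t scale is the 0.95 quantile of the studentized range (3 groups, 48 df) divided by √2: 3.420/1.414 = 2.418. For a standardized difference d, the power of one pairwise contrast is the probability that a noncentral t with 48 df and noncentrality d√(n/2) exceeds 2.418 in absolute value. Here √(17/2) = 2.915.

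**Step 1. Try to reproduce 84.6% from the printed ceramide inputs**

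d = 0.041/0.02 = 2.05, and the noncentrality is 2.05 × 2.915 = 5.98. Tukey power is **99.97%**, not 84.6%.

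Other tests on the same inputs also exceed 99.9%: an unadjusted t test (32 or 48 df), the normal approximation (one- or two-sided), Bonferroni, the overall F test, and a paired t test. Inflating the SD by √2, in case .02 is not an SD of change, still gives 96.1% with Tukey.

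**Step 2. What 84.6% would need**

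Solving for Tukey power of 84.6% gives d ≈ 1.185. With a change of 0.041 that is an SD of 0.041/1.185 ≈ 0.035, about 1.73 times the printed SD. With an SD of 0.02 it is a change of 0.02 × 1.185 ≈ 0.024. Neither value is in the plan. Doubling the SD to 0.04 gives 84.8% with an unadjusted two-sided normal approximation, but the plan states neither that SD nor that test, and Tukey power at that SD is 71.4%.

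**Step 3. What can be said for DAG**

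Without a DAG change and SD, only a range by assumption is possible. At 17 per arm with Tukey at 5%:

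| Assumed DAG difference (SD of change) | Pairwise power |
|---|---|
| 0.5 | 18% |
| 0.8 | 47% |
| 1.0 | 69% |
| 1.12 | 80% |
| 1.185 | 84.6% |
| 1.5 | 97% |
| 2.05 | 99.97% |

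A second view starts from the printed ceramide ratio and supposes that the SD of DAG relative to its change is larger by some factor. Power is then 98.9% at 1.25 times, 93.7% at 1.5 times, 71.4% at 2 times and 49.4% at 2.5 times. The documents do not say which factor applies.

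**The case against.** A reader might infer that the trial is underpowered for DAG. The documents do not show that. If the standardized DAG difference is above about 1.185, power exceeds 84.6%; if the plan meant a change as large as ceramide's in SD units, power would be near 100%. A reader might also infer that 84.6% was computed from the ceramide change and SD and then carried over. Step 1 speaks against this, since those inputs do not give 84.6%. Where the figure came from cannot be established.

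Three further points are fair. DAG does have a power statement for another analysis: the correlation with insulin sensitivity, based on r = -0.45 in Figure 2B, with 92% power at n = 51. That stands, but it is not a power for group comparisons. Second, the figures are not visible here, and section I refers to preliminary data in a research strategy that is not part of this document, so a sarcolemmal DAG pilot change may exist. No readable text or caption mentions one, so the point is limited to what the plan prints. Third, the plan sets no rule for interpreting a null DAG result, so the misreading described above is a risk and not a stated intention.

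Reading the claim as a similar change in SD units does not rescue it. That would be a further assumption, which the plan neither states nor supports for DAG.

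**Conclusion.** The concern holds in two parts. First, 84.6% is unsupported for the Di-C18:0 DAG primary outcome, because no change or SD of change for sarcolemmal DAG appears in the readable text. DAG power is unknown; across assumed differences of 0.5 to 1.5 SD it runs from 18% to 97%. Second, the figure disagrees with the ceramide inputs beside it, which give 99.97%. To reach 84.6% the ceramide SD would have to be about 0.035 where .02 is printed.

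These results assume 17 completers in each arm, equal variances, no change in controls, a two-sided 5% Tukey test with 48 df, and, for ceramide, that .02 is the SD of change. The mismatch does not hinge on sidedness or on the choice among the tests tried. The defect is one of justification and internal consistency; it does not show that the sample size is too small.

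**What to change.** In section IV.F, Aim 1:

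1. Remove the 84.6% claim for DAG. State instead that 17 completers per arm with Tukey at 5% give 80% power for a between-arm difference in change of about 1.12 SD, about 69% at 1.0 SD and about 47% at 0.8 SD.
2. State that no pilot SD of change for sarcolemmal DAG was used. If one exists for Di-C18:0 DAG, give it with the expected change and compute the power from them.
3. For C18:0 ceramide, correct either the power or the SD so that they agree, and name the test and sidedness. Confining the existing sentence to ceramide is not enough, because 84.6% does not follow from its inputs.
4. Report the DAG contrasts with confidence intervals, so that a non-significant result is judged by the differences it leaves open.

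The cost is a few sentences of protocol text and a less favourable power statement for DAG. Sample size and procedures do not change.

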Aim 2: Our statistical methods are rigorous with an *a priori* statistical analysis plan to test our hypothesis in an unbiased manner, and power analysis based on our own preliminary data. Data will be analyzed for normality, and any non-normally distributed variables will be log-transformed for use in analytic models. Correlations between the change in mitochondrial/ER DAG and sphingolipid species and the change in insulin sensitivity, mitochondrial respiration, ROS production, acyl-carnitine species, and ER stress will be performed using Pearson's correlations coefficient in the overall study group. Data comparing changes in mitochondrial/ER DAG and sphingolipid species to changes in insulin sensitivity and parameters of mitochondrial respiration between groups before and after the intervention will be analyzed using a oneway ANOVA (SAS statistical software ver. 9.4, Cary, NC). If overall differences are observed by group then individual group comparisons will be made using Tukey's procedure, which corrects for family-wise error rates. Changes in individual DAG and ceramide species will be examined using the Benjamini Hochberg procedure to limit false discoveries, and changes in groups of DAG and ceramide species will be examined using PCA as described in Aim #1. Our power analysis is based on our preliminary data for the change in mitochondrial ceramide and DAG species after the pilot intervention shown in Figures 8 and 10, and assuming there will be no significant changes in the control intervention. With an overall n of 51, we will have 99% power to detect a Pearson correlation coefficient as large as that observed in our preliminary data (Figure 7B, r= -0.44), and we will have 80% power to detect a correlation coefficient as small as -0.38. With an n of 17/group, we will have 95% power to measure a similar change in mitochondrial DAG and sphingolipids as we have observed in our pilot data after the weight loss or exercise interventions using pairwise comparisons in ANOVA models using the Tukey procedure. The type 1 error rate (alpha) will be set at 5% for all comparisons.

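### Aim 2 states 99% power at r = -0.44 with n = 51, but Aim 1 states 92% at the larger |r| of 0.45 with the same n, test and alpha; the stated inputs give about 91%

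*Combined protocol and SAP*

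**What the plan says.** Section IV.F, Aim 2, gives two power figures for the correlation between change in mitochondrial/ER lipids and change in insulin sensitivity and related measures, both for 51 completers. The first is "we will have 99% power to detect a Pearson correlation coefficient as large as that observed in our preliminary data (Figure 7B, r= -0.44"). The second is "we will have 80% power to detect a correlation coefficient as small as -0.38".

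Section IV.F, Aim 1, makes the parallel statement for sarcolemmal lipids: "we will have 92% power to detect a Pearson correlation coefficient similar to our preliminary data (Figure 2B, r= -0.45"). It gives the same second point, 80% at -0.38. The Aim 1 analysis is described as "using Pearson's correlation coefficients in the entire study group (n=51"), and Aim 2 also uses the whole study group. Both aims set the type 1 error rate at 5%. Neither says whether the test is one- or two-sided.

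**The concern.** The two aims share the sample size, the test and the alpha, and they quote the same 80% point. They are therefore on one power curve. On such a curve power increases with |r|, so a correlation of 0.44 cannot have 99% power when 0.45 has 92%. That conflict needs no calculation.

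The figure matters because it is the only power stated for the Aim 2 correlation at the pilot effect size. If r = -0.44 is correct, the chance of missing a true correlation of that size is about 9%, not 1%. If r is the wrong number, the plan misreports the preliminary result on which its power statement rests.

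**Working it through.** **Inputs.** From section IV.F: n = 51, alpha = 0.05, |r| = 0.44 (Aim 2), 0.45 (Aim 1) and 0.38 (both aims). Sidedness is not stated, so both were tried.

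**Simple check (Fisher z, two-sided).** Power ≈ Φ(atanh|r| × √(n − 3) − 1.960), with √48 = 6.928. The opposite tail is negligible.

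- |r| = 0.38: 0.4001 × 6.928 − 1.960 = 0.812, power 79.2%
- |r| = 0.45: 0.4847 × 6.928 − 1.960 = 1.398, power 91.9%
- |r| = 0.44: 0.4722 × 6.928 − 1.960 = 1.312, power 90.5%

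**Exact check (bivariate normal).** Power is P(T > t_crit), where T is noncentral t with n − 2 degrees of freedom and noncentrality r/√(1 − r²) × √Q, averaged over Q ~ chi-square with n − 1 degrees of freedom.

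| \|r\| | Plan states | Exact, two-sided 5% | Exact, one-sided 5% |
|---|---|---|---|
| 0.38 | 80% (Aims 1 and 2) | 80.0% | 87.7% |
| 0.45 | 92% (Aim 1) | 92.4% | 96.0% |
| 0.44 | 99% (Aim 2) | 91.1% | 95.2% |

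The two-sided test reproduces the 92% and both 80% figures, and the one-sided test reproduces none of the stated figures. Only the 99% fails two-sided, by 99 − 91.1 = 7.9 percentage points. Simulation with 200,000 draws gives 91.0% at 0.44. A fixed-predictor noncentral t, the most generous of the two-sided approximations tried, gives 92.9%.

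**What would give 99%?** Two-sided at 5%:

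- At n = 51, by Fisher z: atanh|r| = (1.960 + 2.326)/6.928 = 0.619, so |r| = 0.550. The exact value is 0.547. Any |r| from about 0.531 upward gives at least 98.5%, which rounds to 99%.
- At |r| = 0.44, n would have to be about 85.
- At |r| = 0.44 and n = 51, alpha would have to be about 0.33.

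**The case against.** The strongest defence is that the 99% came from a different setting. Two candidates exist: a one-sided test, since sidedness is not stated, and the 69 people recruited rather than the 51 completers (section IV.C: "will be screened to recruit sixty-nine obese men and women into the study").

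- One-sided, n = 51: 95.2% at 0.44.
- Two-sided, n = 69: 97.1% at 0.44, but 90.6% at 0.38, where the same sentence says 80%.
- One-sided, n = 69: 98.7% at 0.44, which rounds to 99%, but 94.9% at 0.38.

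None of these gives both figures in the Aim 2 sentence. The last two also contradict its own premise, "With an overall n of 51, we will have 99% power".

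Three points on the other side do stand. First, the direction of the error is unknown. Section III says of Figure 7B only that total ceramide was inversely related to insulin sensitivity, without a coefficient. If the true r is near -0.55, the 99% is right and nothing was overstated. Second, the practical effect is small: power at the stated r remains above 90%, and the other correlation figures reproduce. Third, the 9% miss rate assumes that the pilot relation in Figure 7B carries over to a correlation between changes, which is what Aim 2 tests. That limits how much weight any power figure at this r can bear, but it does not repair the arithmetic.

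**Conclusion.** The concern holds. The 99% and the r = -0.44 cannot both be correct at n = 51 and alpha 5%. The conflict with Aim 1 follows from ordering alone. The size rests on one assumption, a two-sided test, which the plan's other correlation figures support. On that basis power at r = -0.44 is 91.1% (90.5% by Fisher z), and if that r is right the plan overstates power by about 8 percentage points.

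This is a wrong number in the power justification, and it should be corrected. It does not show an underpowered correlation analysis. The per-group comparisons with 17 per arm were not examined under this point.

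**What to change.** Check the coefficient against Figure 7B, then correct whichever number is wrong in the Aim 2 power sentence of section IV.F.

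- If r = -0.44 is confirmed, replace 99% with 91%.
- If r is the misprint, correct it and restate the power for the corrected value. The 99% can remain only if the corrected |r| is at least about 0.53, where power rounds to 99% (99.0% needs about 0.55).

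Stating that the correlation tests are two-sided would make the figures reproducible from the text.

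The cost is one look at a figure and one changed number. Sample size, endpoints and analysis stay as they are; this error gives no reason to alter n = 51. If r = -0.44 stands, the plan will show a less favourable power than it does now.
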